### **Ancillary study:**

Analysis plan: We will use standard parametric and nonparametric statistical tests as appropriate (e.g., t-tests, Wilcoxon rank sum) to test the relation between gait and turning measures at home and ADT history, frailty category, faller status, and disability. We will then fit multivariable models (e.g., linear, logistic) to predict each outcome from Smartsox measures while including important control variable such as age, disease severity and comorbidities. Model assumptions will be thoroughly investigated and alternative estimation procedures will be applied should any violations occur.

### **Ancillary study #2:**

**Aim 1:** We will use canonical correlation analysis (CCA) to evaluate relationships between physical and cognitive aging measured at a single timepoint. CCA is a method for evaluating

relationships between two sets of variables; the method is used to generate canonical variates, which represent latent constructs within each group of variables (similar to principal components from a principal component analysis), and canonical weights, which quantify the relative importance of each variable's contribution to each latent construct. We considered alternative analysis methods, such as multivariate multiple regression, but CCA will yield the richest information set and allow us to understand the dimensionality of the relationships between physical and cognitive aging, without defining variables as exposure or outcome. Using CCA will also reduce the likelihood of false discovery; alternative procedures would require running multiple models to investigate all outcomes of interest. We will define two variable sets using measures of physical aging and cognitive aging (see Variable Sets below). Data will be examined for normality, and standard descriptive statistics, including frequencies and measures of central tendency and dispersion where appropriate, will be used to describe the sample. We will examine bivariate relationships between demographic/clinical variables and physical and cognitive aging measures to further characterize the sample. Variables to be included in the CCA will be examined for meeting statistical assumptions, followed by generating canonical correlations for each canonical variate pair. Significantly correlated pairs will be retained and used to construct a series of correlation matrices, through which we will identify the canonical weights of individual variables and their correlation with each canonical variate and member variables. We will identify 1) the degree of shared variance between latent constructs of physical and cognitive aging using likelihood ratio tests (Wilks lambda) on each canonical variate, and 2) the individual variables responsible for the most shared variance using communality coefficients ( $h^2$ ).

**Variable Sets for CCA:** CCA does not require variables to be defined as an exposure or outcome; instead variables are assigned to a conceptually meaningful group. For Aim 1, physical aging (variable set #1) is indexed by objective and perceived mobility, and cognitive aging (variable set #2) is indexed by depression, fatigue, and cognitive functioning. See Table 2 for list of variables and corresponding measures.

**Confounders:** CCA does not accommodate inclusion of potential confounding variables. As part of initial analyses to understand the sample, we will examine bivariate relationships between physical and cognitive aging measures and potential confounders (age, body mass index (BMI), time since diagnosis, cancer stage, and other treatments (e.g. surgery, radiation, chemotherapy)).

**Power and Sample Size:** With a sample size of 284 men and an alpha of 0.05, we will have 80% power to detect a correlation between canonical variates of physical aging and cognitive aging of  $r=0.17$  (small-medium effect size; small  $r=.1$ , medium  $r=.25$ ).

**Aim 2:** As in Aim 1, we will use canonical correlation analysis (CCA) to evaluate relationships between physical and cognitive aging measured at a single timepoint. For Aim 2, we will define two variable sets using measures of physical aging and cognitive aging (see Variable Sets below). Analyses will proceed as in Aim 1.

**Variable Sets for CCA:** For Aim 2, physical aging (variable set #1) is indexed by metrics of daily life mobility, and cognitive aging (variable set #2) is indexed by depression, fatigue, and cognitive functioning. See Table 3 above for list of variables and corresponding measures.

**Power and Sample Size:** With a sample size of 65 and an alpha of 0.05, we will have 80% power to detect a correlation between canonical variates of physical aging and cognitive aging of  $r=0.34$  (medium effect size).

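### Ancillary study #2 sizes shared variance from canonical weights fitted and evaluated in the same men, so retained correlations are optimistic: severely at N=65, modestly at N=284

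*Combined protocol and SAP*

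**What the plan says.** The plan is in section 13.0, Ancillary study #2. For Aim 1 it fits a canonical correlation analysis (CCA) to a physical and a cognitive set of variables. It then filters the pairs: "Significantly correlated pairs will be retained and used to construct a series of correlation matrices". From the retained pairs it identifies "the degree of shared variance between latent constructs of physical and cognitive aging using likelihood ratio tests (Wilks lambda" test on each variate, and it uses communality coefficients to find the variables that account for most of the shared variance. Aim 2 follows the same steps with SmartSox metrics as the physical set.

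The power statements are: "With a sample size of 284 men and an alpha of 0.05, we will have 80% power to detect a correlation between canonical variates" of 0.17 for Aim 1, and "With a sample size of 65 and an alpha of 0.05, we will have 80% power to detect a correlation between canonical variates" of 0.34 for Aim 2.

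The text mentions no shrinkage or bias adjustment, resampling, hold-out sample or confidence interval. On multiplicity it says: "Using CCA will also reduce the likelihood of false discovery".

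**The concern.** CCA chooses the weights that make the correlation as large as possible in the men at hand. The correlation in those same men is therefore too high on average, and more so with more variables and fewer men. Keeping only significant pairs adds a second upward push. Wilks lambda tests whether an association exists and allows for the number of variables, but it does not bring the estimate back to its population value.

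Size is what this sub-study delivers. The aims in section 2.0 ask for the association between cognitive and physical aging, and the design text in section 3.0 promises to show which measures contribute most. If both answers come unadjusted from the fitting sample, a modest link in 65 men can be published as a strong one, credited to the wrong metric.

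**Working it through.** **Inputs.**
- Sample sizes 284 and 65, alpha 0.05, and correlations 0.17 and 0.34: section 13.0.
- Cognitive set, q = 5 (section 3.0, cognitive aging measures): QLQ-C30 cognitive subscale, FACT-Cog, CES-D, SF-36 Vitality and the fatigue scale.
- Physical set, p: an assumption, 3 to 10. Section 13.0 points to variable tables that are not in the supplied text.

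**The plan's own figures.** For one ordinary Pearson correlation, two-sided, the value detectable with 80% power is r = tanh[(1.960 + 0.842)/√(N − 3)].
- N=284: 2.802/√281 = 0.167, so r = 0.166, which rounds to the stated 0.17.
- N=65: 2.802/√62 = 0.356, so r = 0.342, which rounds to the stated 0.34.

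Both figures reproduce. They describe a single correlation with no fitted weights, so they carry no allowance for optimism.

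**Size of the optimism.** I simulated Gaussian data with one non-zero canonical correlation, fitted CCA, and applied the Wilks test through Rao's F.

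| N | true r (r²) | mean in-sample r | mean r when significant |
|---|---|---|---|
| 65 | 0.34 (12%) | 0.47 (p=3) to 0.60 (p=10) | 0.55 to 0.67 (30% to 45%) |
| 65 | 0.50 (25%) | 0.63 (p=8) | 0.68 |
| 284 | 0.17 (2.9%) | 0.24 to 0.28 (p=4 to 8); 0.30 (p=10) | about 0.29 to 0.32; 0.34 (p=10) |
| 284 | 0.50 (25%) | 0.52 to 0.53 | little bias |

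In Aim 2 the reported shared variance would be about 30/11.6 = 2.6 to 45/11.6 = 3.9 times the true value. In Aim 1 a true 0.17 can cross the plan's own medium mark of 0.25.

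**False positives.** With no true link the Wilks test rejected in about 5% of runs at both sample sizes.

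**Rankings.** At N=65 and true 0.34, one metric carried the whole link. The metric with the largest structure coefficient was the wrong one in 14% to 37% of significant runs. A separate set of runs put the upper end at 39%.

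**What an adjustment does.** One simple form is r²adj = 1 − (1 − r²)(N − 1)/(N − p − q − 1), set to zero if negative.
- N=65, p=8, q=5, average in-sample r = 0.566: 1 − 0.680 × 64/51 = 0.147, so r = 0.38 (true 0.34).
- N=284, p=8, q=5, average in-sample r = 0.282: 1 − 0.920 × 283/270 = 0.035, so r = 0.19 (true 0.17).
- N=65, p=8, q=5, average r among significant runs = 0.643: 1 − 0.587 × 64/51 = 0.264, so r = 0.51.

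The first two lines show that the adjustment removes most of the fitting bias. The third shows that it does not remove the effect of selecting on significance.

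At N=65 and true 0.34, the root mean squared error is 0.15 to 0.27 for the in-sample value, about 0.13 to 0.14 after shrinkage, and 0.26 to 0.32 for the cross-validated value. Shrinkage gains almost nothing with 3 metrics and roughly halves the error with 10.

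**The case against.** The best defence is that the plan does not report whatever the fit produces. It tests each pair first, with a test that accounts for the number of variables, and that test holds its level. This stands. A reader might infer that absent links will look strong. The documents do not support that, because about 95% of analyses with no true link would retain no pair. What remains is the rare false positive, which at N=65 with 8 metrics would average 0.62.

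A second point also stands. The two aims should not be treated alike, and 0.17 and 0.34 are minimum detectable values rather than expected ones. Bias shrinks as the true correlation rises, and at N=284 it is small at 0.50.

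Third, cross-validation might seem the natural replacement for the size. It is not, because it measures how well the fitted weights predict in new men. With 5 folds and 8 metrics it averages 0.10 for a true 0.34 at N=65, and 0.06 for a true 0.17 at N=284. At these values it lies further from the truth than the in-sample figure.

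Fourth, the false-discovery sentence is a fair remark about one multivariate analysis against many models, and nothing here rebuts it. It simply does not extend to effect size or rankings.

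Last, the number of metrics is assumed, and the plan's own tables may set a short list. That would reduce the bias without removing it: with 3 metrics at N=65, a true 0.34 still averages 0.47.

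**Conclusion.** The concern holds as a bias in the size of retained canonical correlations and in the ranking of variables. It is not a fault in the test's error rate. It is severe in Aim 2, where a true 12% shared variance would be reported as about 30% to 45% when significant. It is modest in Aim 1, where a true 0.17 averages 0.24 to 0.28 with 4 to 8 metrics.

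The figures assume 5 cognitive and 3 to 10 physical variables, Gaussian data and one non-zero canonical correlation. Correlation among variables within a set does not change the canonical correlations, but it would change the ranking figures, which assume independent metrics. The sub-study is a cross-sectional secondary analysis, so the trial's falls endpoint is unaffected.

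**What to change.** In section 13.0, Ancillary study #2, Aims 1 and 2:

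1. Report a shrinkage-adjusted canonical correlation and shared variance as the size of association, and name the formula in advance. Give it for the first pair whether or not that pair is significant, because adjustment does not undo selection.
2. Give bootstrap intervals for the canonical correlations, loadings and communalities, and word any ranking of variables in the light of them.
3. If cross-validated correlations are shown, label them as the performance of the fitted weights in new men, and say that they fall below the population value.

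The Wilks tests and the false-discovery sentence can stay. The cost is a few sentences and analysis code, with no new data. The reported correlations will be smaller and the intervals wide, especially with 65 men.

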## **Ancillary study #2:**

### **Design**

We will use two complementary secondary analyses to characterize relationships between physical and cognitive aging in men with prostate cancer treated with ADT, based in a model of cancer treatment- induced accelerated aging. **Aim 1** will use baseline data from the GET FIT Prostate clinical trial (N=284) to investigate associations between cognitive aging (cognitive functioning, depression, fatigue) and physical aging (objective and perceived mobility). **Aim 2** will use baseline data from a subset of participants in GET FIT Prostate who completed additional assessments of physical aging at home using wearable sensors (daily life mobility; N=65). From

Aims 1 and 2, we will have a unique opportunity to characterize cross-sectional relationships among latent domains of physical and cognitive aging and to identify which measures are the most interrelated and strongest contributors to the observed associations.

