### **Conceptual Framework**

According to Carroll et al.'s model of cancer treatment-related accelerated aging, physical and cognitive aging are driven by cancer treatment-induced cellular stress/damage and systemic inflammation. In this model, physical aging manifests as mobility impairment and increased risk of frailty and comorbidities, while cognitive aging is comprised of both behavioral and cognitive features, including depression, fatigue, and cognitive deficits. This model is based largely on studies of chemotherapy and radiotherapy, but we believe it can also be a model to study the impact of ADT on accelerated aging. Here, we will use this conceptual framework to guide our approach to understanding how ADT leads to interrelated physical and cognitive aging.

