#### Other variables of interest (Aims 1 and 2):

*Demographic* variables and cancer history and treatments will be measured by an in-house questionnaire. Measures that account for disease extent (presence or absence of metastatic disease), type of ADT (intermittent vs. continuous; use of next generation high potency agents) will be collected.

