## 5.0 INCLUSION/EXCLUSION CRITERIA

### Inclusion Criteria:

- Diagnosed with histologically confirmed prostate cancer (confirmed by self-report on Health History Questionnaire. In the case a participant isn't able to confirm this criterion, a letter will be sent to his physician.)
- Currently on ADT for  $\geq 6$  months OR not currently receiving ADT, but received  $\geq 6$ -month course within the last 10 years (confirmed by self-report on Health History Questionnaire. In the case a participant isn't able to confirm this criterion, a letter will be sent to his physician.)
- If they have had other treatment, such as surgery, radiation or chemotherapy, it must have been completed  $\geq 6$  weeks prior to enrollment and no concurrent adjuvant therapy other than ADT for prostate cancer (confirmed by self-report on Health History Questionnaire. In the case a participant isn't able to confirm this criterion, a letter will be sent to his physician)
- Meets criteria for having experienced  $\geq 1$  fall in the last year (confirmed by self-report on Health History Questionnaire) or if no falls, meets criteria for slow TUG time ( $\geq 12.0$  seconds) or slow chair stand time ( $\geq 10.0$  seconds) (confirmed by baseline screening testing)

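### Ancillary study #2 wrongly states that canonical correlation analysis cannot take confounders, so age, which the plan names as a confounder, stays out of the analysis that answers both aims

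*Combined protocol and SAP*

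**What the plan says.** The Confounders paragraph for ancillary study #2 (section 13.0) states that "CCA does not accommodate inclusion of potential confounding variables". It then says: "As part of initial analyses to understand the sample, we will examine bivariate relationships between physical and cognitive aging measures" and a list of potential confounders, namely age, BMI, time since diagnosis, cancer stage and other treatments. No step carries these variables into the CCA. No residualisation, stratification or sensitivity analysis is planned, and Aim 2 follows Aim 1.

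The aims in section 2.0 are worded as associations in men treated with ADT, and the Design text in section 3.0 promises to "characterize cross-sectional relationships among latent domains of physical and cognitive aging". The Conceptual Framework in the same section goes further and speaks of "understanding how ADT leads to interrelated physical and cognitive aging". The background in section 1.0 likewise suggests that ADT accelerates the relationship.

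The eligibility criteria (section 5.0) admit current ADT users and also men "not currently receiving ADT, but received" a course of at least 6 months in the last 10 years. Section 3.0 records that "type of ADT (intermittent vs. continuous; use of next generation high potency agents) will be collected", but no ADT exposure variable is on the confounder list.

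**The concern.** Age plausibly worsens gait, chair stand and balance, and may also relate to cognition, mood and fatigue. If it acts on both sets, an unadjusted CCA can return a significant variate pair that is largely chronological age. The canonical weights and communality coefficients are exposed as well: measures that track age can appear as the strongest contributors, which is one of the things the study wants to identify. A bivariate table can show that age relates to both sets, but it cannot remove age from any of these quantities.

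Rejection in that case is not a false positive for the unadjusted association, which would be real. The problem is interpretation. The framework predicts physical-cognitive coupling through ADT, and ordinary ageing would give the same picture.

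The rest of section 13.0 handles this differently. The parent trial considers age and ADT timing as possible covariates throughout, and ancillary study #1 controls for age, disease severity and comorbidities.

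**Working it through.** **1. The plan's own figure.** The inputs, from section 13.0, are N=284 and N=65, alpha 0.05 and 80% power. For a single bivariate correlation, two-sided, the Fisher z formula is r = tanh((1.960+0.842)/√(N−3)).
- N=284: tanh(2.802/√281) = 0.166, which rounds to the stated 0.17.
- N=65: tanh(2.802/√62) = 0.342, which rounds to the stated 0.34.

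The stated detectable correlations are reproduced. They belong to one bivariate correlation, not to the Wilks test on two sets of variables.

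**2. Whether CCA can adjust.** Regress every variable in both sets on the covariates and run CCA on the residuals. The test uses Bartlett's multiplier N−1−k−(p+q+1)/2 with k covariates, and the chi-square degrees of freedom remain pq. With p=6, q=5 and k=1 the multiplier falls from 277 to 276 at N=284, and from 58 to 57 at N=65. The exposure/outcome-free structure for which the plan chose CCA is kept.

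**3. What age alone can induce.** The documents give no age correlations, and the variable tables that the plan cites are not in the text available. Assumptions: 6 physical and 5 cognitive variables, within-set residual correlation 0.4, and no link between the sets except age. If each of m variables in a set correlates a with age, the total within-set correlation is ρ = 0.4(1−a²)+a², and the share of age explained by the set is R² = m·a²/(1+(m−1)ρ). The population canonical correlation is √(R²₁·R²₂).

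Worked case, a=0.3 in both sets: ρ = 0.454, R²₁ = 0.54/3.27 = 0.165, R²₂ = 0.45/2.816 = 0.160, so the canonical correlation is 0.16.

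Rejection rates of the 5% Wilks test, 2,000 simulated samples per cell (rates differ by about a percentage point between runs):

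| Age correlation, physical / cognitive | Canonical correlation from age alone | Unadjusted, n=284 | Unadjusted, n=65 |
|---|---|---|---|
| 0.2 / 0.2 | 0.08 | 7–8% | 6% |
| 0.3 / 0.3 | 0.16 | 23–24% | 8% |
| 0.4 / 0.4 | 0.27 | 72–73% | 14% |
| 0.3 / 0.1 | 0.06 | 6% | 5–7% |
| 0.4 / 0.1 | 0.07 | 8% | 5–7% |
| 0.3 / 0.2 | 0.11 | 12% | 5–7% |
| 0.4 / 0.2 | 0.14 | 17–18% | 5–7% |

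In the three equal-correlation rows, age-partialled CCA rejected in about 5% to 6% of samples at both sample sizes.

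**4. Cost of adjusting.** Replace √(N−3) by √(N−3−k).

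| Covariates | Detectable r, n=284 | Detectable r, n=65 |
|---|---|---|
| 0 | 0.166 | 0.342 |
| 1 | 0.166 | 0.344 |
| 2 | 0.166 | 0.347 |
| 6 | 0.167 | 0.358 |
| 10 | 0.169 | 0.370 |

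**The case against.** The stated aims claim only association, no planned analysis estimates an ADT effect, and unadjusted CCA answers a purely descriptive question. Age is named and examined, so a reader would see its bivariate links. The cognitive set is entirely self-reported, and nothing in the documents shows that questionnaire scores track age as strongly as performance tests do. The largest rejection rate needs a correlation of 0.4 with age for every measure in both sets. All of this stands, and it limits the size of the point. It does not rescue the reason given for leaving age out.

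Four stronger readings are tempting, and the documents do not support them.
- A reader might infer that ADT exposure was left out because CCA supposedly cannot adjust. The plan gives no reason for that omission; ADT timing, duration and type are simply not on the list.
- A reader might infer that an ADT effect is the stated question. That language is in the background and framework, not in the aims.
- A reader might infer that an age-induced correlation of 0.17 would be declared significant 80% of the time. That power belongs to a single bivariate correlation; in the assumed design the Wilks test rejects about 26% of the time.
- A reader might want every covariate removed in the main analysis. Section 3.0 calls weight gain a common side effect of ADT, so BMI may lie on the pathway of interest. Partialling ADT timing or duration could likewise remove the shared variance that the framework is about.

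**Conclusion.** The point holds. The ground for not adjusting is incorrect, and it keeps a confounder the plan itself names out of the only analysis that answers Aims 1 and 2. At n=284 the consequence runs from slight (about 6% to 8% rejection when the age correlations are weak in either set) to severe (about 72% when every measure correlates 0.4 with age). At n=65 it is small, about 5% to 14%. These rates rest on assumed set sizes, an assumed within-set correlation and assumed age correlations; only the trial's data can say which case applies.

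Adjusting for age would not by itself support attribution to ADT, because every man has been exposed and the data are cross-sectional. The point concerns a secondary analysis and touches no endpoint of the randomised trial.

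**What to change.** Replace the sentence in the Confounders paragraph with the following plan.
- **Age-partialled CCA:** for both aims, residualise both variable sets on age, run the CCA on the residuals with the error degrees of freedom in the Wilks test reduced for the covariate, and report it beside the unadjusted CCA, including weights and communalities.
- **Sensitivity CCA:** also partial ADT timing (current or past) and, at n=284 only, the other listed confounders. State that BMI and ADT exposure may lie on the pathway of interest, so a weaker correlation there does not show confounding.
- **Wording:** state conclusions as association among ADT-treated men, not as an effect of ADT.

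The cost is a few lines of code and a few degrees of freedom. With age alone the detectable correlation is unchanged at 0.166 for n=284 and goes from 0.342 to 0.344 for n=65. Adding ADT timing takes the latter to 0.347. No new data are needed: section 9.0 lists date of birth and the type and dates of cancer treatments among the data collected.

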### **Measures**

#### Physical aging measures (Aim 1):

*Objective physical functioning* will be assessed using measures of slowness, weakness, functional mobility, and functional balance, as described above.

*Perceived physical functioning* will be measured by self-report using the physical function subscale of the European Organization for Research and Treatment of Cancer Quality of Life Questionnaire (EORTC QLQ-C30; version 3, App. I) and the overall functioning subscale of the Late-Life Function and Disability Instrument (LLFDI).

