#### Physical aging measures (Aim 2):

Daily mobility will be assessed using measures derived from SmartSox, including activity, turning, and gait quality/quantity, as described above.

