#### Cognitive aging measures (Aim 1 and 2):

Cognitive functioning will be assessed using cognitive function subscale of the European Organization for Research and Treatment of Cancer Quality of Life Questionnaire (EORTC QLQ-C30; version 3, App. I) and the FACT-Cog Instrument.

Depression will be assessed using the Centers for Epidemiologic Studies Depression scale (CES-D).

Fatigue will be assessed using the self-reported score on SF-36 Vitality Scale and the Functional Assessment of Chronic Illness Therapy (FACT) Fatigue scale.

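### Ancillary study #2: the stated 80% power at r=0.17 and r=0.34 is for one Pearson correlation; for the planned canonical correlation test it is roughly 13–54%

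*Combined protocol and SAP*

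**What the plan says.** Section 13.0, Ancillary study #2, gives one power statement per aim. Aim 1: "With a sample size of 284 men and an alpha of 0.05, we will have 80% power to detect a correlation between canonical variates" of r=0.17, labelled small to medium. Aim 2: "With a sample size of 65 and an alpha of 0.05, we will have 80% power to detect a correlation between canonical variates" of r=0.34, labelled medium. Neither states a power method, the number of variables per set or the number of non-zero canonical correlations assumed.

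The same section specifies the test as "likelihood ratio tests (Wilks lambda) on each canonical variate". For the variables it says "See Table 2 for list of variables and corresponding measures", and it refers to a Table 3 for Aim 2. Those lists are not in the text available to us, and their absence is not counted as an error.

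Section 3.0, Ancillary study #2, does name the measures:

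- **Physical set, Aim 1:** objective function "will be assessed using measures of slowness, weakness, functional mobility, and functional balance", plus two perceived-function scales.
- **Physical set, Aim 2:** "Daily mobility will be assessed using measures derived from SmartSox, including activity, turning, and gait quality/quantity".
- **Cognitive set, both aims:** five instruments, namely the QLQ-C30 cognitive subscale, FACT-Cog, CES-D and two for fatigue ("Fatigue will be assessed using the self-reported score on SF-36 Vitality Scale and the Functional Assessment of Chronic Illness Therapy (FACT) Fatigue scale").

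On confounding, section 13.0 says "CCA does not accommodate inclusion of potential confounding variables". It examines age, BMI, time since diagnosis, stage and other treatments only through bivariate relationships.

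**The concern.** A canonical correlation is the largest correlation obtainable between weighted sums of two sets of variables, with the weights chosen from the data. Even with no true association, its sample value is well above zero. A valid test must allow for that fitting, so the overall Wilks test spends p × q degrees of freedom, where p and q are the set sizes. A power figure that ignores p and q describes a different test.

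As written, readers would believe that canonical correlations of 0.17 and 0.34 would be found four times in five. A non-significant Wilks test, above all at n=65, could then be taken as evidence that physical and cognitive aging are unrelated.

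The confounding statement raises a smaller, related matter. Age may drive both sets. Without an adjusted analysis beside the unadjusted one, the report cannot show whether the canonical association is more than shared age.

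**Working it through.** **Inputs from the plan.** n=284 and n=65, alpha 0.05, power 80%, r=0.17 and r=0.34, Wilks lambda test (section 13.0).

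**Assumptions.** Set sizes: one score per named domain or instrument in section 3.0 gives about 6×5 for Aim 1 and at least 3×5 for Aim 2. Sets from 2×3 to 15×5 are shown as a range. The data are multivariate normal, and one canonical correlation is non-zero unless stated otherwise.

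**Step 1: reproduce the stated figures.** For one Pearson correlation, two-sided, the detectable r is tanh[(1.960 + 0.842)/√(n − 3)].

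- n=284: tanh(2.802/√281) = 0.166, which rounds to 0.17.
- n=65: tanh(2.802/√62) = 0.342, which rounds to 0.34.

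One-sided testing gives 0.147 and about 0.305, which do not match. The stated figures are therefore two-sided Pearson figures. In CCA terms they hold only for one variable per set.

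**Step 2: the planned test.** Λ = ∏(1 − rᵢ²) over the sample canonical correlations. Rao's F is [(1 − Λ^(1/s))/Λ^(1/s)] × df2/df1, with

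- df1 = pq
- s = √[(p²q² − 4)/(p² + q² − 5)]
- df2 = [n − 1 − (p + q + 1)/2]·s − pq/2 + 1

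For 6×5 at n=284: s = √(896/56) = 4, df1 = 30, and df2 = 277 × 4 − 15 + 1 = 1094. The signal is about nρ²/(1 − ρ²) = 284 × 0.0289/0.9711 = 8.45. On one degree of freedom that gives about 82% power. Spread over 30 it gives about 25–26% (noncentral F).

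**Step 3: simulated power** (6,000 datasets per setting; rejection under the null 4.4–5.6%):

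| Sets (p×q) | n=284, ρ=0.17: one root | two equal roots | n=65, ρ=0.34: one root | two equal roots |
|---|---|---|---|---|
| 2×3 | 54% | 88% | 52% | 85% |
| 3×3 | 46% | 82% | 44% | 79% |
| 3×5 | 38% | 72% | 33% | 68% |
| 6×5 | 26% | 56% | 22% | 49% |
| 8×5 | 23% | 48% | 19% | 41% |
| 10×5 | 20% | 43% | 16% | 36% |
| 15×5 | 16% | 35% | 13% | 26% |

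Independent repetitions agreed within about 4 percentage points. Using Roy's largest root in place of Wilks lambda changes one-root power by only about 0–4 points.

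**Step 4: canonical correlation detectable with 80% power, one root.**

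| Sets | n=284 | n=65 |
|---|---|---|
| 2×3 | 0.22 | 0.44 |
| 3×5 | 0.25–0.26 | 0.51 |
| 6×5 | 0.29 | 0.57 |
| 8×5 | 0.31 | 0.61 |
| 10×5 | 0.32 | 0.63–0.69 |
| 15×5 | 0.35 | 0.69 |

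The 3×5 entry at n=284 and the 10×5 entry at n=65 come from two noncentral F approximations; the others are simulated.

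**Step 5: a plain check.** With no association at all, the mean largest sample canonical correlation is 0.23 at n=284 (6×5) and 0.38 at n=65 (3×5). Both exceed the values the plan calls detectable.

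**Step 6: cost of covariate adjustment.** Partial CCA on k covariate degrees of freedom behaves as CCA at n − k. The 80% detectable value moves from 0.289 to 0.294 with 7 df (n=284, 6×5). At n=65 (3×5) it moves from 0.511 to 0.516 with age only, or to 0.540 with 7 df. With association arising only from a shared age factor, the age-adjusted test rejected in 4.8–5.0% of simulated datasets.

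**The case against.** The strongest reply is that the size of the shortfall rests on inputs the plan does not give. The set sizes are inferred: 2×3 counts one variable per broad domain, and 15×5 has no basis in the text. This stands as a limit on the percentages. It does not rescue the claim, because one-root power is near 50–55% even at 2×3.

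Second, the plan wants to learn the dimensionality of the relationship, so several non-zero roots may be in view. With three equal roots, overall Wilks power is about 79% at n=284 (6×5) and 88% at n=65 (3×5). That is correct, but section 13.0 states no such scenario. It names one correlation, and its value is the single-correlation value.

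Third, canonical correlations are maximised over weights, so true values may well exceed 0.17. Suppose every cross-set correlation is 0.17 and every within-set correlation is 0.3. Then 6×5 sets have a canonical correlation of 0.17 × √30/√(2.5 × 2.2) = 0.40, and power at n=284 is above 99%. This stands: the stated minimum is wrong, but Aim 1 is not shown to be underpowered for effects that may occur. Aim 2 has less room. In 3×5 sets under the same within-set assumption, cross-set correlations of about 0.25 are needed for roughly 80% power: 0.25 × √15/√(1.6 × 2.2) = 0.52.

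Fourth, ordinary CCA has no covariate term, the aims are descriptive, and aging is itself the target. That supports keeping the unadjusted analysis as the main result. It does not make bivariate checks a substitute for adjustment. The plan for the first ancillary study already adjusts its SmartSox models for age.

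**Conclusion.** Wrong as written. Both power figures are correct for a single two-sided Pearson correlation and do not apply to the planned Wilks test. At the stated values, with one non-zero canonical correlation, power is about 20–26% for Aim 1 (10×5 to 6×5) and 19–33% for Aim 2 (8×5 to 3×5). The full range over the set sizes tried is 13–54%. With two equal roots, 80% is reached only at 2×3 for both aims and at 3×3 for n=284; 3×3 at n=65 gives 79%.

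The mismatch of method is certain. The percentages depend on the assumed set sizes, the number of roots and multivariate normality. The statement that CCA cannot take confounders is true only of the basic method, and it is the lesser point. Everything here is confined to ancillary study #2, which is a secondary analysis of data already collected.

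**What to change.** 1. Replace both power sentences with the power of the Wilks lambda test for the actual number of variables in each set, and state how many non-zero canonical correlations are assumed. If one is assumed, give the detectable value: about 0.29–0.32 at n=284 (6×5 to 10×5) and about 0.51–0.61 at n=65 (3×5 to 8×5), or the figure for the final variable lists. Leave n unchanged.

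2. Replace the sentence on confounders with, for example: *Beside the unadjusted CCA we will report a partial CCA in which both variable sets are residualised on age and, where n allows, on BMI, time since diagnosis, cancer stage and other treatments, with degrees of freedom reduced by the number of covariates.* Present it as a co-reported result, not as the main one.

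The cost is some wording and a few lines of code, with no new data. The stated detectable effects become less favourable. Adjustment itself takes little power, except that at n=65 a full covariate list takes more than age alone.
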